2.8 Stereotactic focused ultrasound CL thalamotomy

More recently, Jeanmonod *et al.* achieved bilateral central lateral thalamotomy ablations with submillimeter precision⁷⁹ for therapy resistant neuropathic pain syndromes using focused ultrasound.⁵⁴ Mean pain relief using a visual analog scale was reported as 49% at 3 months, and 57% at one year. There was a single thalamic hemorrhage resulting in neurologic morbidity, and this complication led to the universal adoption of cavitation detectors in the technology.⁸⁰

2.9 Rationale for this study: focused ultrasound medial thalamotomy for the trigeminal and other craniofacial neuropathic pain syndromes

Contemporary MR guided focused ultrasound is capable of delivering high intensity energy through the intact human skull with precision to deep brain targets. Thalamic lesions have been created within 1-2 millimeters of accuracy^{79,81} and temperature monitoring of the focus and surrounding brain is possible with a resolution of $\sim 1^{\circ}$ Celsius.⁸²⁻⁸⁷ A recent international, randomized, controlled trial in 76 patients resulted in FDA approval of the ExAblate Neuro in July 2016.⁸⁸ Please see Appendix B for a list of prior investigations using ExAblate Neuro.

Medial thalamotomy for pain should represent an iterative advance in the use of MR-guided FUS where the medial thalamic (CL) target is less associated with eloquent structures than the ventrolateral thalamus. This cohort of treatment-resistant craniofacial neuropathic pain is intended to represent a severe pain condition with few treatment options. The etiologies may be diverse but the pathophysiology for the development of neuropathic pain is more homogenous and results from peripheral injury/ neuropathy to cranial nerves or those of the head and neck.

We intend to exclude trigeminal neuralgia where neural function is preserved and may represent a different pathophysiology than the other neuropathies included. Similarly, craniofacial pains from malignancy will be excluded as many of these manifest a nociceptive component, and the primary investigation here is for neuropathic pain.

This proposed pilot study has several innovative aspects:

1. Painful, trigeminal neuropathy and other craniofacial pain syndromes are ideal conditions for investigation of pain relief because:
 - A relatively homogenous disorder resulting from injury or pathophysiology of a cranial nerve.
 - Associated neuropathic pain is notoriously refractory to medical therapies

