NOTE: All procedures for both arms are the same to this point. Below is the description of treatment for ExAblate Arm. The Sham will be identical except that the energy will be turned to 0.

18. A central point in the targeted area will be targeted with a low dose, sub-lethal energy level sonication to confirm the targeting accuracy on the MR images. Focal point position and/or transducer location will be adjusted as necessary. The bilateral lesioning will be planned and executed as follows:

- a. Stereotactic planning of both (left and right) medial thalamic targets will be performed on the ExAblate Neuro workstation in the pre-planning phase. The central lateral thalamic nucleus CLT nucleus will be targeted by stereotactic coordinates in reference to the midcommissural point of the ACPC line.
 - b. If the pain symptoms are asymmetric or unilateral, the CLT nucleus contralateral to the most symptomatic side will be treated first. The acoustic energy will be escalated in a series of incremental sonifications until a therapeutic ablation of temperature of 60-65°C is reached by peak voxel, MR thermometry. The second, ipsilateral CLT target will then be treated with the same protocol.
 - c. If the pain symptoms are symmetric, the nondominant CLT will be treated first. The dominant side CLT will be treated as the second target.
19. To enhance the procedure safety and mitigate some of the inherent risks of thermal lesioning of brain tissue:
 - a. The thalamotomy treatment will be performed as a series of sonifications with small increments in power within the designated target volume.
 - b. The subject will be examined periodically by the clinical team for neurologic signs and symptoms.
 - c. Sonication will start with low energy prior to permanent thermal ablation. This is to ensure the planned sonication to be centered on the CL nucleus of the Thalamus. Low energy sonication will non-destructively warm the target. The warming will be captured by the MR thermometry and the MR thermal images will be displayed in real time to the treating physician. The physician will then verify that the warming is centered on the anatomic target. This will allow the centering of the eventual permanent thermal lesion in the correct location, in the center of the CL nucleus of the Thalamus.

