Perioperative confusion has infrequently been observed with medial thalamotomy procedures. Jeanmonod reported one case of somnolence from 96 Radio Frequency (RF) CL thalamotomies¹⁰⁰ and no occurrences when the lesions performed with FUS.⁵⁴ The risk of this almost certainly increases with older age. In order to mitigate the risks of perioperative confusion or cognitive decline, subjects will undergo preoperative psychological assessment to gauge their cognitive reserve exclude those with significant cognitive impairment. The precise delivery of acoustic energy with MR-guidance will ensure that lesions are not delivered outside of the targeted CL nuclei – a technology that much less susceptible to confounding features like brain shift or stereotactic inaccuracies. MRgFUS has been shown consistently with submillimeter precision.^{79,81}

Symptomatic intracerebral hemorrhage with stereotactic procedures has been consistently estimated to range from 1 to 2%, and may be slightly higher with pallidotomy procedures which have been reported in large series to almost 4%. Intracerebral hemorrhage from stereotactic RF lesions likely occurs in a slightly higher fashion than stereotactic FUS lesioning because electrode penetration of the brain is required. In order to mitigate the risk for intracerebral bleeding from FUS, subjects with severe hypertension and coagulopathy will be excluded from trial participation, and normotension will be maintained throughout all procedures.

In the RF ablation experience of the PI, out of a series of 94 radiofrequency lesioning procedures for movement disorders, a single 10-mm thalamic hemorrhage was noted in a subject undergoing thalamotomy at a probe tip temperature of 70°C. (unpublished data) It is difficult to translate the probe tip temperature in an RF lesion to the target volume temperature of an MRgFUS lesion, but it may be postulated that thermal lesioning at higher temperatures could increase the risks of hemorrhage. In order to minimize such risk, we propose to perform permanent ultrasound lesioning bilaterally with a measured temperature of 65°C at the target. This temperature is sufficient for thermal coagulation of the target but well below the peak temperature observed in the case cited above. The experience of the ExAblate TcMRgFUS thalamotomy in the treatment of subjects with neuropathic pain and Essential tremor entailed treatment to 65°C at target without any observed neurologic or hemorrhagic consequences.

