Cavitation. More recently, Jeanmonod et al. achieved central lateral thalamotomy ablations with submillimeter precision⁷⁹ for therapy resistant neuropathic pain syndromes using focused ultrasound. There was a single thalamic hemorrhage resulting in neurologic morbidity which possibly occurred from cavitary effects. This complication led to the universal adoption of cavitation detectors in the ExAblate technology.⁵⁴

Delayed ischemic infarction has been rarely observed with stereotactic RF lesioning of the basal ganglia. The occurrence of this complication has been only reported in 3 of 50 cases of RF pallidotomy, and these cases occurred in subjects with a significant history of vasculopathy

identified either clinically or radiographically.¹⁰¹ These ischemic events occurred in a delayed fashion at 10, 51, and 117 days following the procedure. One of 89 subjects undergoing subthalamotomy presented with a delayed onset of involuntary movements at one week and imaging suggested a thalamic/subthalamic infarction¹⁰² It is postulated that these delayed infarctions results from damage to the perforating of vessels of the basal ganglia. Lenticulostriate perforating vessels are much less prevalent in the medial thalamus. Subjects at risk for bleeding (low clotting factors or anticoagulants) are excluded. In addition, heating should seal vessels.

Infection has been rarely observed with stereotactic lesioning and certainly with less frequency than occurs with implanted devices from DBS procedures. We anticipate a negligible risk for meningitis or brain abscess with ExAblate thalamotomy as this is not an open brain procedure requiring incisions or burr holes through the skull.

Mortality. There have been no mortalities in over 400 ExAblate Neuro ablations performed worldwide. The mortality rate with surgical radiofrequency thalamotomy, a much more common procedure that has been employed for decades, has not been reported and likely occurs in much less than 1% of cases. At the University of Virginia, over 100 radiofrequency thalamotomies have been performed without mortality.

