Appendix A

Neurosurg Focus 32 (1):E1, 2012

Transcranial magnetic resonance imaging-guided focused ultrasound: noninvasive central lateral thalamotomy for chronic neuropathic pain

[name].,^{1,2} BEAT WERNER, M.Sc.,³ ANNE MOREL, PH.D.,^{1,4}
LARS MICHELS, PH.D.,^{1,3} EVAL ZADICARIO, M.Sc.,⁵ GILAT SCHIFF, B.Sc.,⁵
AND [name].³

¹Department of Functional Neurosurgery and ²Center for Clinical Research, University Hospital Zürich;

³Center of Ultrasound Functional Neurosurgery, Solothurn; ⁴MR-Center, University Children's Hospital, Zürich, Switzerland; and ⁵InSightec, Ltd., Tirat Carmel, Israel

Object. Recent technological developments open the field of therapeutic application of focused ultrasound to the brain through the intact cranium. The goal of this study was to apply the new transcranial magnetic resonance imaging-guided focused ultrasound (tcMRgFUS) technology to perform noninvasive central lateral thalamotomies (CLTs) as a treatment for chronic neuropathic pain.

Methods. In 12 patients suffering from chronic therapy-resistant neuropathic pain, tcMRgFUS CLT was proposed. In 11 patients, precisely localized thermal ablations of 3–4 mm in diameter were produced in the posterior part of the central lateral thalamic nucleus at peak temperatures between 51°C and 64°C with the aid of real-time patient monitoring and MR imaging and MR thermometry guidance. The treated neuropathic pain syndromes had peripheral (5 patients) or central (6 patients) origins and covered all body parts (face, arm, leg, trunk, and hemibody).

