Results. Patients experienced mean pain relief of 49% at the 3-month follow-up (9 patients) and 57% at the 1-year follow-up (8 patients). Mean improvement according to the visual analog scale amounted to 42% at 3 months and 41% at 1 year. Six patients experienced immediate and persisting somatosensory improvements. Somatosensory and vestibular clinical manifestations were always observed during sonication time because of ultrasound-based neuronal activation and/or initial therapeutic effects. Quantitative electroencephalography (EEG) showed a significant reduction in EEG spectral overactivity. Thermal ablation sites showed sharply delineated ellipsoidal thermolesions surrounded by short-lived vasogenic edema. Lesion reconstructions (18 lesions in 9 patients) demonstrated targeting precision within a millimeter for all 3 coordinates. There was 1 complication, a bleed in the target with ischemia in the motor thalamus, which led to the introduction of 2 safety measures, that is, the detection of a potential cavitation by a cavitation detector and the maintenance of sonication temperatures below 60°C.

Conclusions. The authors assert that tcMRgFUS represents a noninvasive, precise, and radiation-free neurosurgical technique for the treatment of neuropathic pain. The procedure avoids mechanical brain tissue shift and eliminates the risk of infection. The possibility of applying sonication thermal spots free from trajectory restrictions should allow one to optimize target coverage. The real-time continuous MR imaging and MR thermometry monitoring of targeting accuracy and thermal effects are major factors in optimizing precision, safety, and efficacy in an outpatient context.

(<http://thejns.org/doi/abs/10.3171/2011.10.FOCUS11248>)

KEY WORDS • central lateral thalamotomy • neuropathic or neurogenic pain • transcranial magnetic resonance imaging-guided focused ultrasound

CONSIDERING the inherent risks related to neurosurgical procedures, such as infections and hemorrhages, there is an obvious demand for less invasive alternative procedures. Following extensive preclinical investigations,^{4–6,10,11,13,15,24,25,31,32} a clinically relevant pro-

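### Section 9.5 supports the 65°C target with a no-consequences statement that the protocol's own neuropathic pain series contradicts, and the 9.8.1 list leaves out deficits reported in Appendix B

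*Protocol*

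**What the plan says.** In its discussion of intracerebral hemorrhage, Section 9.5 allows that hotter lesions may bleed more often and then fixes the temperature: "we propose to perform permanent ultrasound lesioning bilaterally with a measured temperature of 65°C at the target". Two supports follow. One is that 65°C lies below the 70°C probe-tip temperature of a single bleed in the investigator's radiofrequency series, a comparison that the section itself calls hard to translate to focused ultrasound. The other is that the ExAblate experience in neuropathic pain and essential tremor "entailed treatment to 65°C at target without any observed neurologic or hemorrhagic consequences".

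Other parts of the protocol describe the neuropathic pain experience as follows.

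- Section 2.8: "There was a single thalamic hemorrhage resulting in neurologic morbidity, and this complication led to the universal adoption of cavitation detectors".
- Section 9.5, the Cavitation paragraph that comes next: "There was a single thalamic hemorrhage resulting in neurologic morbidity which possibly occurred from cavitary effects".
- Appendix A (abstract of the pain series): 11 patients were ablated "at peak temperatures between 51°C and 64°C". The one complication was "a bleed in the target with ischemia in the motor thalamus". It led to two measures: "the detection of a potential cavitation by a cavitation detector and the maintenance of sonication temperatures below 60°C".

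On the temperature to be used here, Section 6.5 item 18b escalates energy "until a therapeutic ablation of temperature of 60-65°C is reached by peak voxel, MR thermometry". Item 19d of the same section titrates up to 60°C over a 5 mm diameter. The end of Section 9.8 gives peak voxel temperatures of 55 to 65°C.

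Section 9.8 bases its side-effect list on experience with the 650 KHz system. The neurological deficits that 9.8.1 gives as reported so far are vestibular signs, paresthesias and dysesthesias or pain. Appendix B, on a 650 KHz pain study of 19 subjects with the same central lateral target, reports one event comprising gait disorder, motor neglect, dysarthria and right-hand dysmetria.

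**The concern.** The Section 9.5 sentence is a statement of fact about safety, and it is used to justify the temperature of a permanent bilateral brain lesion. In the body text it is the only sentence that sets a focused ultrasound temperature against an outcome. If it is wrong, the argument for 65°C rests on the radiofrequency comparison alone.

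Section 9.0 says that the risks described in Section 9 are those explained to subjects at consent. The consent form is not at hand, so what subjects are actually told cannot be checked, but the source text for it should be right. Safety is also the primary outcome of the study (Section 3.2), and the 9.8.1 list is the protocol's summary of the deficits already seen on this device.

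**Working it through.** No power or sample-size figure is involved. The check sets the statements side by side.

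1. **Same experience.** Section 9.5 cites the neuropathic pain experience with ExAblate. Section 2.8 describes that series with mean pain relief of 49% at 3 months and 57% at one year. Appendix A gives the same two figures. The bleed in Section 2.8 and the one in Appendix A therefore come from one series.

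2. **Event count.** Section 9.5 claims 0 neurologic or hemorrhagic consequences. Section 2.8, the Cavitation paragraph of 9.5 and Appendix A each report 1 bleed, and the first two say that it caused neurologic morbidity. Appendix B reports 1 neurological deficit event, which may be the same one. The count is at least 1, not 0.

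3. **Can the wording be rescued?**
   - If the sentence means treatment up to 65°C, the series with peaks of 51-64°C falls inside it, and so does the bleed.
   - If it means treatment at 65°C, none of the 11 ablated patients in Appendix A reached it, so that series gives no support. Appendix B has 19 subjects, 19 - 11 = 8 more, and gives no temperatures for them.
   - Neither reading makes the sentence true and also useful as support for 65°C. The essential tremor half cannot be checked, because the protocol does not tabulate adverse events for it.

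4. **Response to the bleed.** Appendix A names 2 measures. Where Sections 2.8 and 9.5 recount the response, they mention only the detector. A limit close to the second measure does appear in Section 6.5 item 19d, but it is not linked to the bleed, and the other temperature statements do not follow it.

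5. **Temperature statements.**

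| Place | Temperature |
|---|---|
| 6.5 item 18b | 60-65°C, peak voxel |
| 6.5 item 19d | up to 60°C within a 5 mm diameter |
| 9.5 | 65°C measured at the target |
| 9.8, closing paragraph | 55-65°C, peak voxel |

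Item 19d may use a different measure from item 18b, but the protocol does not say so. Item 18b and Section 9.8 use the same measure and still differ at the lower end. No reason is given for going above the below-60°C measure.

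6. **Deficit list.** Signs in the Appendix B event: 4. Signs named in the 9.8.1 list: 0. The vestibular entry might be thought to overlap gait disorder. Dysmetria, dysarthria and motor neglect have no counterpart in that list.

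**The case against.** The best defence is that Section 9.5 lists thermal hemorrhage and cavitation as separate primary risks. The sentence closes the thermal discussion, and the next paragraph reports the bleed under cavitation. Hemorrhage, infarction, off-target damage and serious deficit are also disclosed in Sections 9.4, 9.5, 9.7 and 9.8. On this view one qualifying clause is missing and nothing more.

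Much of that stands. The bleed is not hidden, and a reader who inferred concealment would be wrong, since it is reported three times. The defence does not make the sentence true. It excludes any neurologic or hemorrhagic consequence, without limiting this to thermal causes, and the cavitation attribution is only a possibility.

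A reader might also infer that 65°C is unsafe, or that the protocol ignores the 60°C limit altogether. The documents support neither. The temperature at which the bleed occurred is not given, detectors are now fitted to all systems (Section 9.4), and item 19d carries a limit of up to 60°C. The difference between a 64°C peak and a 65°C target has no weight of its own, because Section 2.9 puts thermometry resolution at about 1°C.

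Finally, a reader might infer that the short 9.8.1 list changes which events would count as unexpected and so stop the study. The documents do not support that. Section 10.1 does not tie unexpectedness to 9.8.1, and the definition of an unanticipated device effect in Section 10.0 looks to the whole investigational plan, which includes Appendix B.

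**Conclusion.** The Section 9.5 sentence is wrong as written: it claims no events, and the protocol's own sources show at least one bleed with neurologic morbidity in the experience it cites. The 9.8.1 list is incomplete by four named signs, or by three if gait disorder is counted as vestibular. The treatment temperature is stated in four ways that do not agree.

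This is an inconsistent and understated risk justification. It is not evidence that 65°C is unsafe, and it gives no usable event rate: the series is small, it predates cavitation detectors, and the Appendix A and Appendix B events may be one and the same. The conclusion rests only on the protocol text and on taking Section 2.8 and Appendix A to describe one series, which their matching results support. Severity is minor to moderate.

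**What to change.** - **Section 9.5.** Replace the sentence with the actual experience. For example: in the focused ultrasound neuropathic pain series (11 patients ablated, peaks 51-64°C), one patient had a bleed at the target with motor thalamic ischemia and neurologic morbidity, possibly from cavitation; a cavitation detector was then introduced and temperatures were kept below 60°C. Report the essential tremor experience in a separate sentence.
- **Treatment temperature.** State one temperature, with its measure (peak voxel or over a stated diameter), and use it in 6.5 items 18b and 19d, 9.5 and 9.8. If it exceeds the below-60°C measure, give the reason in a sentence. Which value to use is a clinical decision, and this point does not ask for a lower one.
- **Section 9.8.1.** Add dysmetria, dysarthria, motor neglect and gait disorder to the deficits reported so far.

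The cost is text editing and one decision on temperature. The downside is a less favourable risk statement, which may lead some candidates to decline. No visit, endpoint or sample size changes.

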9.6 Risks Related to the Sonication Pathway

Skin: The treatment set-up process includes filling the gap between the ultrasound transducer and the skull with a water-filled membrane to provide acoustic coupling. There is a possibility of small air bubbles remaining attached to the skin. These could cause a small focal hot spot and cause local pain or a burn to the scalp. The active cooling mechanism unique to this system is designed to reduce the risk of skin burns and improve subject comfort. In previous studies, MRgFUS treatments have caused burns of the skin (see analysis above). To minimize this risk, the scalp will be carefully shaved, and scars or other irregularities (e.g. eczema) will be kept outside the treatment pathway. Subjects with remarkable atrophy and poor healing capacity of the scalp (> 30% of the skull area traversed by the sonication pathway) will be excluded from this study.

Skull and air-filled spaces: In the treatment planning, air-filled spaces (frontal, ethmoid, sphenoid sinus, mastoid) inside the skull are identified in bone window CT images and kept outside the pathway. Other irregularities of the skull, which might scatter the acoustic energy, are compensated for in the system. Skull may become heated by absorbing more acoustic energy than normal soft tissue. The skull cannot sense pain but the overlying soft tissues may sense pain if the bone becomes heated. MRI thermometry at 1.5 T is able to detect changes of ± 3 Celsius in soft tissues¹⁰³. Possible heat transfer from the skull bone to the brain by successive sonifications is monitored by MRI thermometry of the cortex and white matter. The sonication duration and energy levels, and the cooling times between the sonifications are adjusted so that the focus in the target tissue is heated while allowing other tissue to cool down between sonifications. Local bone damage is very unlikely because the active cooling mechanism system is designed to keep the bone temperature below a temperature that can damage it. Based on the data acquired to date and reviewed by FDA under G020182/S04, the average temperature rise at the skull level ranges

between 1 to 5 Celsius. Hence, this active cooling strategy should continue to provide the safety needed.

Dura, meningeal arteries and venous sinuses: The dura adjacent the skull may absorb heat if the bone becomes heated. Dura itself may sense pain and the main branches of the arteries are sensitive to heat. The meningeal arteries can generally be avoided in the treatment planning as their grooves in the skull are visible in 3D-CT. Local necrosis of the dura is unlikely, and were it to happen, it would not cause cerebrospinal fluid leakage. The venous sinuses between the two leaves of the dura, the sagittal sinus, the straight sinus and the transverse sinus may be in the sonication pathway. Their heating will be avoided by the active cooling sub system. The sigmoid sinus and the cavernous sinus will be kept outside the pathway due to their proximity to the skull base and cranial nerves, respectively.

Subarachnoid space: Cerebrospinal fluid in the thin subarachnoid space between the dura and the cortex could possibly transfer heat from bone to the cortex. There is no specific risk to the CSF itself becoming heated. Because it can flow within the subarachnoid space, this can serve as another mechanism to prevent local hot spots next to the skull.

Cortex: In prior studies of ExAblate lesioning of thalamus for tremor, nearly one hundred subjects have been treated without any neurological or imaging evidence of cortical effects. All subjects have been assessed posttreatment with MRI, and there have not been detectable changes outside of the treatment area.

Brain, cranial nerves and cerebral arteries: In this study the treatment path will avoid cranial nerves and major cerebral arteries (ICA, MCA, ACA, BA).

Micro-calcification: The subject population of this study may have some level of micro-calcification present in the brain tissue. Given calcium's higher absorption of ultrasound energy, its presence may create additional heating effect along the beam path. This risk is mitigated by utilizing the CT data (to localized the calcified areas) and the various tools of the ExAblate system to delineate these areas so that the beam is blocked from passing through these calcified areas.

Secondary Hot Spots: theoretically speaking, there is a potential risk due to secondary hot spots that may occur along the beam path outside the focus. This has been reported in the literature for different types of transducer configurations using similar frequencies. The ExAblate system, with its unique, highly focused transducer configuration, was tested extensively using advanced simulations. The results of this work showed no evidence of significant hot spots away from the focal area. In any case, the real time thermal imaging feedback samples the entire field of view around the targeted tumor. These thermal images are displayed during the course of the energy delivery and therefore if there is evidence of any secondary hot spot is observed, the treating physician will be able to utilize the other specific feature of the ExAblate system that is "real-time" stop sonication button that instantaneously halts energy delivery. Hence, if this risk exists, the system is well equipped to handle it in real time and prior to incurring any tissue damage.

